NWC mobile app. Findings from our IDIs informed the content to include in our mobile app. The app contains six sessions; these sessions include content on alcohol use, birth control and safer sex, and facts of AEP and FASD. The app also includes culturally relevant imagery such as the medicine wheel and connections across generation. Motivational interview elements of tone, assessment of personal risk, decisional balance exercises, and goal setting are also included. Participant knowledge of alcohol and birth control methods, including condoms, is assessed through the app. See Appendix A for a selection of images from the App.

IV. Research Methods

We propose using an RCT with a baseline sample n=700 urban AIAN young women aged 16 to 20 to evaluate NWC for its effectiveness in AEP prevention.

Figure 1. NWC Conceptual Model

Outcome Measure(s): Figure 1 depicts the measures used the assess the impact of NWC. These measures include demographics, such as age, education level, and income, measures of social risk; environmental support; and cultural identity. Theoretical mediators include knowledge of effective contraception and alcohol use during pregnancy and self-efficacy related to sexual activity and contraceptive and alcohol use. Our primary outcomes include sexual activity, abstinence, effective contraceptive

use, and alcohol and other substance consumption—AEP protective and risk factors. With the pandemic, we have also added measures on experiences with COVID-19 to capture appropriate context.

B. Description of Population to be Enrolled:

Our population of focus will be AIAN women, ages 16-20, who live in urban areas (50,000 people or more), and who are not pregnant or breastfeeding at the time of enrollment. Currently, we are awaiting approval from the Southcentral Foundation of Alaska, a research review IRB for Alaska Native healthcare in

Anchorage (the only urban area in Alaska with population > 50,000). Until we receive this approval, we will exclude residents from Alaska.

C. Study Design and Research Methods

Screening

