Obtaining informed consent. Preliminary conversations with our university IRB have confirmed that, like our other projects, this project will also likely qualify for a waiver of parental consent for minors, based on minor participants' ages (16-17) and the sensitive nature of the topic wherein participants may incur risk if participation is disclosed to a parent. Participants will be asked to consent to project participation as adults. During the consent process, participants can contact the project team with any questions or concerns. The consent process will describe the 2 arms of the study and let them know that after they complete the baseline survey, their assignment to a particular arm will be random. After reading the consent, participants will be asked follow-up questions to verify comprehension.

Consent

Once the identity is confirmed, the respondent will be sent a unique link (exclusive to that participant) to the consent. Once they have read the consent (which they can scroll up or down for review) they will be asked to electronically sign the form in a signature box if they consent. The participant can take as long as they would like to review the consent or discuss with others. They are able to click on the consent link at a later time if they want to think about their participation. If they consent, we will ask them to write or type their name indicating they agree to an electronic signature and that they consent. We include as a part of the consent that they can take a screenshot or video screen recording of the signed consent form for their

records, or they can request a copy be sent to them by email or USPS. We will ask them for a mailing address (optional, unless they request a USPS-delivered signed consent), and social media handles. These latter contact data are helpful as backup for multiple options to contact participants over the course of the 12 month study should cell number and email no longer work. If they do not consent, they will not be able to participate in the study.

The contact information and consenting signature will be stored in a secured database separate from survey data, and accessible only by project staff.

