Intervention and survey progression. After the baseline survey, participants will be asked to download the app using their email and a password, so we can track their registration and ultimately link app use with survey data (e.g., to check number of sessions responded engaged in). We will incentivize the app download with a small e-gift card (\$10). Once registered, the app will randomize participants and they can immediately begin their first intervention sessions (NWC or counterfactual). Once participants have progressed through their respective programs, each will be given an additional small e-gift card (\$10), and, 2 months later, a URL for the first posttest. Similarly, at 6 and 12 months after program completion, each will be sent URLs to complete a survey.

We will regularly monitor electronic reports of progress through the intervention (for NWC), and survey completion progress for follow-up (both arms). Survey data will be routinely checked by the Data Management team for any problems, inconsistencies, or missing data. They will routinely summarize response rates for each survey, and by arm. If response rates are low, or unbalanced by arm, Drs. [name] and [name] will identify possible causes, their solutions, and quickly implement changes to rectify deficiencies.

D. Recruitment

The primary method of recruitment will be through multiple social media platforms. Specific recruitment activities will vary across the platforms, but will typically include posts to promote the program and study. We will also use seed recruitment, and encourage AIAN young women participants to invite their peers and family members to sign up for the program (i.e., chain referral, up to 3).

We will ask the participants enrolled in the study to follow our page on Instagram, share our recruitment post on their Instagram page and tag us in that post. This strategy will amplify our recruitment post among their followers (who may be similarly eligible) and encourage participation in our study (as the recruitment post will have come from a trusted source). This is completely voluntary and the recruitment post does not require participants to disclose any personal health information.

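### The waiver of parental consent rests partly on risk if a parent learns of participation, yet 16-17-year-olds are among those asked to follow, repost and tag the study publicly on Instagram

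*Combined protocol and SAP*

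**What the plan says.** Four parts of section IV of the combined protocol bear on this.

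- **B, Description of Population to be Enrolled.** "Our population of focus will be AIAN women, ages 16-20". Minors aged 16 and 17 are therefore in the trial.
- **C, Obtaining informed consent.** After preliminary talks with the university IRB, the protocol states that "this project will also likely qualify for a waiver of parental consent for minors". The grounds are the minors' ages and the sensitive topic, on which "participants may incur risk if participation is disclosed to a parent".
- **D, Recruitment.** Enrolled participants will be asked to "follow our page on Instagram, share our recruitment post on their Instagram page and tag us in that post". The purpose is stated: "This strategy will amplify our recruitment post among their followers (who may be similarly eligible"). The protocol adds that the request is voluntary and that "the recruitment post does not require participants to disclose any personal health information". No age limit is given.
- **E, Description, Risks and Justification.** The only risk discussed is that electronic data could be hacked, together with the storage and access controls against it. Section N repeats this text for the interview supplement.

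**The concern.** The consent section identifies one particular harm to minors: a parent finding out that they take part. The recruitment section then asks the same minors to link themselves to the study in a place that their followers can see. The safeguard about health information answers a different risk, because the harm named in the consent section is disclosure of participation, whatever health details are or are not given.

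What is at stake is whether a recruitment step works against part of the stated reason for enrolling 16-17-year-olds without a parent's consent. An IRB considering that waiver would reasonably want the two sections to agree.

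**Working it through.** No figure is stated or disputed, so there is nothing to recompute. The check is to set the sections side by side.

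1. **Are minors asked?** Section B enrols ages 16-20. Section D addresses the request to enrolled participants and makes no exception by age. So 16-17-year-olds are asked.

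2. **What is the harm named in the consent section?** Disclosure of participation to a parent. It is one of the stated grounds for the waiver, beside age and topic. The waiver itself is described as likely, not as granted.

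3. **What does the Instagram request reveal?** Each act taken alone is open to anyone: a non-participant could follow the page or share the post. Taken together, the follow, the repost on her own page and the tag tie a named young woman to the study. Section D expects the repost to work because followers will trust the person it comes from, so the method relies on followers making that link. Participation can be inferred, although it is not stated.

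4. **Who sees it?** The participant's followers. Section D hopes that some are eligible but does not deal with parents or other relatives who may follow the account.

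5. **Do the stated safeguards cover this?** There are two.
   - *No health information required.* This does not bear on disclosure of participation.
   - *Voluntary.* This does bear on it, but it protects a minor only if she realises what the posts may reveal. Section D does not say that she is told.

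6. **Does the risk section cover it?** No. Section E is confined to hacking and stored data.

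7. **Can the number affected be sized?** It would be: minors enrolled × share who comply × share with a parent among their followers × share of those parents who infer enrolment. None of the four terms is given. If enrolment were even across the five year-ages (an assumption), the first term would be 2/5 × 700 = 280; if 20% were minors, it would be 0.20 × 700 = 140. These are counts of minors who could be asked. The other three terms remain unknown, so no estimate of the number exposed follows.

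**The case against.** The strongest reply is that the request is voluntary. Asking for parental consent would necessarily tell a parent, whereas an optional post leaves the decision with a young woman who knows who follows her. On this view the waiver rationale and the Instagram request can both stand. There is force in this: the request does not force disclosure and does not by itself defeat the waiver. It does not close the gap, because section D gives no caution about relatives among followers and section E does not recognise the risk.

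A second reply is that the recruitment post circulates through other channels too, and sharing it is not an announcement of enrolment. This also stands. A reader might infer that every participant who complies is identified as enrolled to all her followers; the documents support only that followers could infer it. The wording of the post is not shown, so how revealing the association would look is unknown.

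Three further inferences are tempting and are not supported.

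- *That the post is aimed at family.* Family members are mentioned under chain referral, a separate route limited to 3 invitees who are to sign up themselves. Eligible relatives would be females aged 16-20, and no text targets parents.
- *That the shared page causes contamination between arms.* Allocation and content are delivered inside the app, and following a page shows neither.
- *That exposure at home leads to drop-out or under-reporting.* Section F says that all measures are self-reported without independent checks, but nothing in the documents links Instagram sharing to retention or candour.

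Finally, the consent form is not part of the text reviewed, so it cannot be said that a warning is missing from it.

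**Conclusion.** The inconsistency is real and limited. The consent section names disclosure of participation to a parent as a risk to minors. The recruitment section asks minors, with everyone else, to take public steps from which followers could infer participation, and the risk section does not consider this.

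The conclusion rests on three things: that the absence of an age limit in section D means what it says; that a follow, repost and tag together make inference possible; and that a minor's followers may include a parent. The last is an assumption, though a modest one.

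The size in participants cannot be estimated. Sample size, power and error rate are untouched. The point merits action because it concerns the protection of minors and the remedy is cheap.

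**What to change.** 1. In section D, limit the public follow, share and tag request to participants aged 18 or over.
2. Offer 16-17-year-olds, and any older participant who prefers it, a private screener link to forward, worded neutrally so that it does not mark the sender as a participant.
3. In section E, add disclosure of participation through social media as a risk, with the steps taken against it.
4. Check that the consent form says that following or tagging the study page may reveal participation, and add this if it does not.

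A sentence in D or E acknowledging the risk would reconcile the text on its own, but it would leave minors being asked to post publicly; the age limit removes that request.

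The cost is an IRB amendment to sections D and E, and to the consent form if needed, with somewhat fewer referrals from minors' public posts. The study's own social-media posts, flyers, listservs, community events and chain referral all remain.

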Fetal Alcohol Spectrum Disorders (FASD) result in neurodevelopmental deficits and lifelong disability; they are a leading cause of preventable birth defects in the U.S.^{1,2} According to the CDC, any sexually active woman of reproductive age who drinks alcohol and does not use effective contraception is at risk for an alcohol exposed pregnancy (AEP) that could cause FASD.² By this definition, American Indian and Alaska Native (AIAN) young women are especially vulnerable. AIAN girls initiate alcohol use earlier than their non-AIAN peers;³⁻⁶ they are also more likely to have used alcohol in their lifetimes, in the last 30 days, and on a daily basis. Concomitantly, compared to all other race groups, high school-aged AIAN girls report the highest levels of ever having had sex (69%), and having had sex in the last 3 months (50%). Across all AIAN youth, 32% reported using alcohol or drugs before last sex, the highest rate across all race groups, and 80% reported not using effective contraception at last sex.89 Unsurprisingly, the birth rate for AIAN women ages 15-19 is 27 per 1000—the third highest rate after non-Hispanic Blacks and Hispanics. 10 One study estimates that 25% of these teen births are substance involved, with the most common substance, alcohol, accounting for more than half of these. 11 While an estimated 72% of AIAN young women live in urban areas, 12 research relevant to AEP is largely based on reservation samples. 13-15 With rare exceptions, 16-20 the research base for urban AIAN youth and young adults remains thin. Urban AIANs tend to live not in concentrated neighborhoods but rather dispersed across the urban landscape; thus, common community-based recruitment and intervention strategies are expensive or rarely applicable for research engagement of urban AlANs.²¹ Consequently, urban AlAN needs are often ignored in research aimed at developing, implementing, and evaluating culturally appropriate services. Recent research indicates that mobile health (mHealth) interventions are promising for delivering effective interventions to hard-to-reach populations.²²⁻²⁴ The goal of this project is thus to expand reach and services to urban AIAN young women through mHealth technology to prevent AEP and FASD.

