The proposed project builds directly on the work of an earlier NIAAA-funded project (R21AA17596; [name], PI (Ojibwe, MPI on this project)). Using intensive community-based participatory research (CBPR) methods, 25,26 tribal community and AEP prevention experts guided the adaptation of CHOICES (Changing High-risk alcohOl use and Increasing Contraception Effectiveness Study),²⁷ an evidence-based brief AEP intervention supported by the CDC, for use with young American Indian women age 16-20. CHOICES relies on motivational interviewing (MI) to increase contraceptive use and decrease drinking among adult women at risk for an AEP. 27 The adapted version, American Indian Youth CHOICES (AIY-C) preserves the brief MI format and focus on AEP prevention through increased contraceptive use and decreased drinking. AIY-C diverges from CHOICES in its cultural content, its universal approach, and its youthful age range. AIY-C supports all young AIAN women in making current (for sexually active or drinking youth) or future (among abstinent youth) healthy choices about contraception and drinking. AIY-C contains features that make it highly amenable to mHealth approaches, including a framework for integrating diverse cultural teachings, few modules of short duration, and concrete opportunities for goal-setting and achievement. This proposed project is innovative in its plan to recruit AIAN young women from major urban areas in the US through social media and to deliver AIY-C via mobile devices—both of which are increasingly ubiquitous among AIAN young adults.^{28,29} While social media recruitment and mHealth interventions are not new,

including for adult AEP prevention,³⁰⁻³³ only very recently have they been used with AIAN populations.³⁴⁻³⁶ Appropriate partnership with urban AIAN organizations is foundational to the project's success.³⁷ We have engaged strong collaborators to guide us through social media recruitment strategies, mHealth intervention translation and implementation, and evaluation processes in urban AIAN settings. Engaging with cultural and intervention expert guidance, we propose the following specific aims:

- SA1: **Develop social-media-based recruitment strategies** for urban AIAN young women; we will pilot and refine these strategies.

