G. Data Analysis Plan:

All intervention effectiveness analyses will be based on an intention-to-treat approach. For continuous outcomes (frequency/quantity indices of alcohol) and mediational outcomes (alcohol and contraceptive self-efficacy), we will estimate a series of latent growth curve models (LGCM) in Mplus to assess the effect of intervention exposure on the trajectories of those outcomes over the study period. The "normative" trajectory of an outcome is estimated for the comparison group before estimating the same trajectory among those exposed to the intervention. The third step estimates the degree to which the normative growth trajectory is altered by intervention exposure. On the fourth and final step, the interaction between intervention exposure and pre-intervention status on the outcome is tested. This permits an assessment of the differential effectiveness of the intervention as a function of baseline levels of the outcome variable.

For dichotomous outcomes, Latent Markov Models (LMM) will be used to evaluate transitions between behavioral states (e.g., sexually active to abstinent) throughout follow-up. 166,167 Intervention status is modeled as a time-invariant covariate; its effect on the transition probabilities is estimated freely. Effectiveness is indicated if those in the intervention have significantly lower probabilities than the controls of transitioning out of the abstinence state and significantly higher probabilities of transitioning out of the sexually active state. LMM may also reveal that early sexual experience among control group participants predicts sexual activity across the course of the study but that this relationship is interrupted among intervention participants. Other moderators of intervention effectiveness will also be explored (e.g., enculturation).

H. Summarize Knowledge to be Gained:

If successful, the overall study will generate evidence of NWC effectiveness for AEP prevention by demonstrating: 1) increased effective contraceptive use or sexual abstinence among urban AIAN young

women; 2) decreased or eliminated alcohol use in urban AIAN young women who drink; and 3) maintained abstinence (sexual or alcohol) among those who have this as their goal. If successful, the project will also provide vital information about the feasibility of mHealth interventions for reaching urban AIAN young women or other urban AIAN populations who might otherwise not access health information or interventions

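### Section G's single abstinence state mixes women who have never had sex with experienced women who are not currently active; with arm the only covariate specified on the transitions, the arm effects can be distorted

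*Combined protocol and SAP*

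**What the plan says.** Section G (Data Analysis Plan) of the combined protocol and SAP assigns latent Markov models to dichotomous outcomes: "Latent Markov Models (LMM) will be used to evaluate transitions between behavioral states (e.g., sexually active to abstinent) throughout follow-up". On covariates it says "Intervention status is modeled as a time-invariant covariate; its effect on the transition probabilities is estimated freely". The success rule has two parts. The first reads "Effectiveness is indicated if those in the intervention have significantly lower probabilities than the controls of transitioning out of the abstinence state", and the second asks for a higher chance of leaving the sexually active state in the intervention arm.

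Sexual history enters only as a possible finding: "LMM may also reveal that early sexual experience among control group participants predicts sexual activity across the course of the study", with the suggestion that the intervention may interrupt this link. Other moderators, with enculturation as the example, are to be explored.

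The trial has no entry criterion on sexual activity, and the opening section says "AIY-C supports all young AIAN women in making current (for sexually active or drinking youth) or future (among abstinent youth) healthy choices". So never-active, paused and active women are all enrolled. Section G does not give the number of latent states, the indicators per wave or any constraint on the error part.

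**The concern.** The plan's own example of a transition runs from active to abstinent. The abstinence state must therefore hold women returning from activity as well as women who have never had sex. Leaving it means first sex for one group and resumption for the other, and those chances are unlikely to be equal. Section G itself expects early experience to predict later activity.

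Two problems can follow.

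- The make-up of the abstinence state can drift apart between arms during follow-up, so the arm contrast on leaving it partly reflects who is in the state.
- If the latent model has one self-report per wave and free error rates, it learns about error mainly from women who go back and forth. It can then label a real pause as a misreport.

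Both parts of the success rule are contrasts of these transition probabilities, so both are exposed.

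**Working it through.** There is no figure in the plan to reproduce here. The only sample-size numbers are 700 enrolled and 525 final (525/700 = 0.75). No alpha, power, effect size or transition rate is given.

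**Inputs from the documents.** 69% of high-school AIAN girls have ever had sex and 50% in the last three months (opening section); N = 525; surveys at baseline and at 2, 6 and 12 months after the program (section C), so four waves. The payment text in section C can be read as five surveys; I used four.

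**Assumed.** The high-school figures apply to this sample; 1:1 allocation; two-sided 5%; equal rates over the unequal intervals; per-interval debut 10%, resumption 50%, pausing 20% in the comparison arm; arm odds ratio 0.6 for leaving abstinence (log -0.51, same in both abstinent groups) and 1.67 for leaving activity (log 0.51); no misreporting.

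**Starting mix.** Never 100 - 69 = 31%; paused 69 - 50 = 19%; active 50%. Experienced share of the abstinence state = 19/(31 + 19) = 38%.

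**Why pooling distorts, by hand.** In the intervention arm the odds ratios turn debut into 6.25%, resumption into 37.5% and pausing into 29.4%.

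- Interval 1, exit from the pooled state: comparison 0.62 x 0.10 + 0.38 x 0.50 = 0.252; intervention 0.62 x 0.0625 + 0.38 x 0.375 = 0.181. Log odds ratio = -1.51 - (-1.09) = -0.42. The gap from -0.51 is only the usual averaging property of odds ratios.
- Start of interval 2, comparison: never 0.31 x 0.90 = 0.279; paused 0.19 x 0.50 + 0.50 x 0.20 = 0.195; paused share 41%.
- Start of interval 2, intervention: never 0.31 x 0.9375 = 0.291; paused 0.19 x 0.625 + 0.50 x 0.294 = 0.266; paused share 48%.
- Interval 2, pooled exit: 0.265 against 0.212. Log odds ratio = -1.31 - (-1.02) = -0.29. The further shrinkage arises because the intervention creates more paused women, who leave abstinence quickly.

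**Model fits.** Maximum likelihood on the exact response-pattern probabilities, with robust standard errors at N = 525:

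| Two-state model | Leaving abstinence (truth -0.51) | Leaving activity (truth 0.51) | False 'reports abstinent while active' rate (truth 0%) |
|---|---|---|---|
| Arm only, free error rates | -0.27 (SE 0.26) | 0.91 (SE 0.31) | 14% |
| Arm only, no error part | -0.32 | 0.51 | none modeled |
| Arm + baseline ever-had-sex, free error rates | -0.50 (SE 0.21) | 0.60 (SE 0.22) | 5% |
| Arm + baseline ever-had-sex, no error part | -0.51 | 0.51 | none modeled |

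In the first model, a comparison-arm woman reporting active, abstinent, active, active has a 90% posterior chance of being classed as active during her real pause.

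**Range.** With resumption 30-70% and pausing 10-30%, the false error rate is 5% to 25%. With debut and resumption both 30%, the false error rate is 0% and every model recovers -0.51.

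**Type I error.** With no arm effect on either transition, rejection stays at 5%. If only leaving activity truly changes, the arm-only latent model shows a spurious log odds ratio of about +0.17 for leaving abstinence, with about 9% rejection.

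**The case against.** The strongest reply is that the plan never specifies the model tested here. Sexual activity is only an example, and the number of states, the indicators and the error part are all unstated. The titles of the cited methods papers mention mixed latent Markov models, which could absorb this heterogeneity. The phrase about other moderators suggests that sexual experience may at least be explored. All transition rates are assumed. This stands as a limit on certainty. It does not remove the point: two named states are the natural reading of a dichotomous outcome, the plan commits to no mixed model, and pooling distorts leaving abstinence even without an error part.

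Three stronger readings are tempting and not supported.

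- A reader might infer that the plan will treat pauses as misreports. That needs free error rates on a single indicator, which the documents do not state, and different exit rates for the two groups.
- A reader might infer that the main harm is lost power, especially for leaving activity. Section G evaluates transitions throughout follow-up, and over three intervals the loss depends on the rates. In the base case, power is 83% for the arm-only latent model against 86% for an error-free model with sexual history, because the inflated estimate offsets its larger SE. At debut 8%, resumption 45% and pausing 20% against 30%, it is about 69% against 90% using reported states. Distortion of the effect is the firmer finding.
- A reader might conclude that reported states should replace the latent model as the main result. Section F says all measures are unverified self-report. With 5% misreporting each way, reported pausing of 20% against 30% becomes about 25% against 34%, a difference of 8.8 points instead of 10. That is a trade-off, not a correction.

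**Conclusion.** The point holds in conditional form. Section G pools never-active and paused women and specifies only arm on the transitions. If those groups leave abstinence at different rates, an arm-only two-state model understates the effect on leaving abstinence: -0.27 or -0.32 against -0.51 in the base case. With free error rates it also overstates the effect on leaving activity (0.91 against 0.51) and reads some real pauses as error.

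Part of the shortfall for leaving abstinence is the averaging property of odds ratios. The rest comes from the state's make-up diverging between arms.

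The sizes rest on assumed rates, on high-school figures applied to ages 16-20, and on an inferred model structure. With equal exit rates nothing is lost, though section G's own expectation about early experience points the other way. This is a cheap improvement to the analysis, not a flaw that invalidates the trial.

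**What to change.** In section G, keep the latent Markov model and do one of two things:

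- include baseline ever-had-sex and baseline age as covariates on the transition probabilities; or
- split the abstinence state into never had sex (cannot be re-entered) and experienced but not currently active.

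The covariate version leaves a small residual (5% false error, 0.60 against 0.51 for leaving activity), because women who have first sex during follow-up and then pause are still pooled. The split handles them directly.

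State the number of states, the indicators and the constraints on the error rates. Report the reported-state version without an error part as a sensitivity analysis, not as the main result.

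The cost is one or two extra parameters per transition and a few sentences in the plan. Age is already asked at screening. An ever-had-sex item must be in the baseline survey: section G's reference to sexual experience implies one, but the documents do not list it, and the phrase could mean activity at early waves. That should be confirmed first.
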